Camp Lejeune. This coincided with a change in the laboratory method and was unlikely to be the onset of contamination. Because there were no water quality standards for the detected VOCs in 1982, and the source of the contamination was not identified, no action was taken until approximately 2 years later.

In July 1984, Camp Lejeune began sampling wells in the Hadnot Point area as part of the base Superfund program. Contaminated wells were closed soon after they were identified in January and February 1985, and a routine sampling program was implemented at all distribution systems on the base. Notable contamination has not been detected in Camp Lejeune's drinking water systems since February 1985.

There were several sources of contamination. The on-base sources included: (a) leaking underground storage tanks containing trichloroethylene (TCE), (b) spills from operations at the vehicle maintenance area, and (c) drum disposal at sites 6, 9, and 82 and associated storage lots at operating unit 2 (ATSDR 1997). The off-base source consisted of a leaking, above-ground, tetrachloroethylene (PCE) storage tank and solvent disposal practices at ABC One-Hour Cleaners, a dry cleaning establishment (ATSDR 1990).

Three water distribution systems provided water for Camp Lejeune's family base housing areas: the Tarawa Terrace, Holcomb Boulevard, and Hadnot Point systems. Because it was not known when the contamination started in each of the distribution systems, chemicals could have been present in the systems for many years before their initial discovery in 1982.

- I **Tarawa Terrace.** Contamination at this water system occurred as a result of disposal practices at ABC Cleaners, which opened in 1954 and was located off-base just outside the gate from Camp Lejeune. The establishment disposed waste solvent in their septic tank system and the ground. In 1958, a drinking water supply well was drilled on-base by the Marine Corps. This well was located 900 feet from the dry cleaners. It is likely that this well was contaminated soon after it was drilled because of its proximity to the source of contamination and the high permeability of soils in the area (ATSDR 1998). Sampling of the finished water at the Tarawa Terrace system began in 1982, and high levels of PCE

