were found (76 ppb – 104 ppb); this range is based on four samples collected during May-July 1982 with a mean of 85.5 ppb. PCE is a dry cleaning solvent. In the one sample taken in 1985 before the contaminated wells were shut down, a PCE level of 215 parts per billion was found. In addition, TCE, a degreaser, and 1,2-dichloroethylene (DCE), a breakdown product of PCE were also detected in this sample. The contaminated wells were closed in February 1985 (ATSDR 1997).

! **Hadnot Point.** This water distribution system supplied water primarily for industrial purposes at the base but it also supplied drinking water to the Hospital Point housing area. High levels of TCE (a maximum of 1,400 ppb) were detected during sampling in 1982. High levels of TCE and DCE were found during the routine testing of the drinking water system in 1984 and 1985. The Hadnot Point system has 39 operational wells, although only approximately 20 wells were used at any one time. The contamination was linked to leaking on-base underground storage tanks.

[**Holcomb Boulevard.** In 1972, the Holcomb Boulevard system went on-line and served the Midway Park, Berkeley Manor, Watkins Village, and Paradise Point areas of base housing. Before 1972, the Holcomb area was served by the Hadnot Point water distribution system. In early 1985, a fuel line accidentally burst at the Holcomb Boulevard water distribution system, releasing fuel into the water supply. To remediate the problem, the Holcomb water supply was provided by an emergency line from the Hadnot Point system. The emergency hookup occurred over a 12-day period starting on January 27, 1985. During this period, the Holcomb area base housing received contaminated water from the Hadnot Point system. Once the fuel line was repaired, the emergency hookup from Hadnot Point was disconnected, and the Holcomb Boulevard system resumed service to its designated housing areas.

Each of the affected housing areas received water containing a mixture of several contaminants, a phenomenon noted with almost every population exposed to contaminants released from hazardous

waste sites.

ATSDR's 1997 public health assessment (PHA) for Camp Lejeune found that PCE was the primary contaminant at ABC One-Hour Cleaners (ATSDR 1997). PCE and other solvents from the dry cleaning establishment had contaminated a nearby well on Camp Lejeune property that provided drinking water to the Tarawa Terrace family base housing.

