- an OR of 5.15 or greater can be detected for 12 cases with leukemia and 444 controls and an OR of 4.3 or greater can be detected for 15 cases with leukemia and 450 controls.

An exposure prevalence of 40% is from the previous study of SGA at Camp Lejeune (ATSDR 1998; Sonnenfeld et al. 2001). It represents the percent of births born at Camp Lejeune that were estimated to ever have been exposed to PCE during the study period. Although we will not know for sure until after the water modeling is completed, it is expected that about half of the births were exposed to PCE. It is also expected that the levels of exposure to PCE varied over the study period such that there will be a significant range of exposures to PCE. The situation for TCE is less clear, and probably a large majority of the births were not exposed to TCE. Again, the TCE levels will vary over the study period so there will be a range of exposures.

All 79 children with the following confirmed or pending birth defects and childhood cancers who were born to parents residing at Camp Lejeune during their pregnancy between 1968 and 1985 will be recruited for the study: 28 NTDs, 36 oral cleft defects, and 15 leukemias. We expect a 90% participation rate because all of the participants took part in the Camp Lejeune Survey in 1999-2002 and gave permission to be contacted for future studies. Additionally, many survey participants have telephoned ATSDR to request the results of the survey and inquire about future studies. A 90% participation rate will yield 71 cases: 25 NTDs, 32 oral cleft defects, and 14 leukemias. Using one control group, we will attempt to enroll ten times as many controls as cases which will yield a comparison group of 710 children to allow

enough controls for the analyses.

Enrollment of Study Participants

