All electronically entered information obtained from questionnaires will be reviewed for missing data and ambiguous responses. Individual interviewers will be contacted to complete missing data where possible or to call back participants to fill in the missing information. Internal consistency and validity programs will be used to identify and correct coding and data entry errors. Data entry will be verified for accuracy by using software data match features.

Reimbursement

No remuneration will be offered to participants. In addition, no invasive procedures will be performed which could potentially cause injury or the need for medical treatment.

Data Analysis

The exposure variables include exposure status, concentration level, and/or percent of water from a contaminated source during specific time periods of interest in the one-year period before the child's birth. TCE and PCE will be evaluated separately. The exposure metrics will be ever/never, a categorization of the contaminant levels, and a categorical exposure variable that incorporates water usage and consumption as well as contaminant levels. Categorical exposure variables will be used because of the uncertainties involved in estimating exposures. We will look at the distribution of contaminant levels to determine appropriate cutoff values for the categorical variables. Those exposed to TCE or PCE will be compared to those without exposure to either chemical in the drinking water. Extensive sensitivity analyses will be conducted on the water modeling.

Descriptive statistics will be presented for the potential risk factors. Verified cases of birth defects and childhood cancers will be compared with controls using unconditional logistic regression. It may be necessary to use exact or conditional logistic regression methods if the data are too sparse. We will consider doing a secondary analysis including unconfirmed cases because the true odds ratio lies between the results obtained by analyzing only confirmed cases and confirmed and unconfirmed cases because unconfirmed cases are not all negative (do not have the condition) or all positive (do have the condition).

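### If Hadnot Point water was already contaminated before 1972, the reference group exposed to neither chemical would hold almost no births from before the Holcomb Boulevard switch, tying the TCE odds ratio closely to calendar period

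*Protocol*

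**What the plan says.** The Data Analysis section of the protocol evaluates TCE and PCE separately, but against one common reference: "Those exposed to TCE or PCE will be compared to those without exposure to either chemical in the drinking water". Cases and controls are compared by unconditional logistic regression, with covariates kept on a 10% change-in-estimate rule. Calendar time is not named as a stratum, restriction or covariate. Controls are a random sample (Eligibility section), with no matching on birth year stated.

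The Introduction describes the water supply. Family housing had three sources: "the Tarawa Terrace, Holcomb Boulevard, and Hadnot Point systems". The third came late: "In 1972, the Holcomb Boulevard system went on-line and served the Midway Park, Berkeley Manor, Watkins Village, and Paradise Point areas of base housing". For the earlier years: "Before 1972, the Holcomb area was served by the Hadnot Point water distribution system". Of Hadnot Point the protocol adds that "it also supplied drinking water to the Hospital Point housing area". On the start of contamination it says only that "chemicals could have been present in the systems for many years before their initial discovery in 1982".

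The Sample Size section plans on 40% of births exposed to PCE, expects about half, and says that "probably a large majority of the births were not exposed to TCE".

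**The concern.** Before the 1972 switch, no family housing area was on a system other than the two later found contaminated. If both were contaminated in those years, a mother living on base in the relevant trimester could hardly count as exposed to neither chemical. The reference group would then come from after the switch. Early Tarawa Terrace births cannot stand in as a same-period comparison for TCE either, because the reference rule excludes anyone exposed to PCE.

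Most TCE-exposed births could then be pre-switch births in the Holcomb housing areas, compared with later births in those same areas. Any difference between the periods in underlying risk, parental reporting or record confirmation would appear in the TCE odds ratio and, diluted, in the PCE odds ratio. This matters because the Data Analysis section bases interpretation on the size of the odds ratio and the exposure-response pattern, not on significance testing alone.

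A larger control sample would not help. Birth year as a covariate helps only partly, because where one period has no unexposed births the model must extrapolate.

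**Working it through.** **The plan's own figures.** The only computed figures are the detectable odds ratios in the Sample Size section. With the continuity-corrected two-proportion formula (two-sided alpha 0.10, 80% power, 40% exposed) I obtain 4.35, 2.85, 3.50, 2.52 and 5.37, against the stated 4.3, 2.85, 3.5, 2.5 and 5.15. They are not in dispute. The protocol gives no births by year or housing area, so what follows rests on stated assumptions.

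**Inputs from the protocol.** Study window 1968-1985 (216 months); switch in 1972, month not given; PCE-exposed share 40% (planning) to about 50% (expected); expected enrolment 32 oral clefts, 25 NTDs, 14 leukemias and 710 controls.

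**Assumptions.** Equal births per month. Tarawa Terrace share T = 40-50%, taken from the PCE share. Hospital Point share H = 1-10%. Switch m = 48 to 59 months after January 1968. Exposure window centred L = 7.5 months before birth (first trimester) or 1.5 months (third). Hadnot Point contaminated from 1968. TCE reaches Hadnot Point users only. The well closures of February 1985 are ignored.

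**Step 1, pre-switch share of births, s = (m + L)/216.**
- First trimester: 55.5/216 = 25.7% to 66.5/216 = 30.8%.
- Third trimester: 49.5/216 = 22.9% to 60.5/216 = 28.0%.

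**Step 2, who is TCE-exposed.** Pre-switch (1-T)s; post-switch H(1-s); reference (1-T-H)(1-s), all of it post-switch. The pre-switch fraction of TCE-exposed births is f = (1-T)s / [(1-T)s + H(1-s)].
- Lowest (T 50%, H 10%, s 22.9%): 0.1146/(0.1146 + 0.0771) = 60%.
- Highest (T 40%, H 1%, s 30.8%): 0.1847/(0.1847 + 0.0069) = 96%.

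**Step 3, bias with no water effect.** Let pre-switch odds be R times post-switch odds. The expected odds ratio is 1 + (R-1)f for TCE and 1 + (R-1)s for PCE. With R = 1.5:
- TCE: 1 + 0.5 × 0.60 = 1.30 to 1. + 0.5 × 0.964 = 1.48.
- PCE: 1 + 0.5 × 0.229 = 1.11 to 1 + 0.5 × 0.308 = 1.15.

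R is illustrative; an R below 1 would bias both downward. With T 40% and H 1-5%, fitting linear birth year to such a cohort (first-trimester window) still left 1.28-1.43 for TCE.

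**Step 4, precision of a post-switch contrast at the null.** The case and control counts cancel, so the SE ratio is √[(1/e_post + 1/r)/(1/e_all + 1/r)], with e the exposed share and r the reference share.
- PCE, low: √[(1/0.385 + 1/0.308)/(1/0.5 + 1/0.308)] = 1.06. High: √[(1/0.277 + 1/0.408)/(1/0.4 + 1/0.408)] = 1.11.
- TCE, low: √[(1/0.0771 + 1/0.308)/(1/0.1917 + 1/0.308)] = 1.4. High: √[(1/0.00692 + 1/0.408)/(1/0.1916 + 1/0.408)] = 4.4.

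Expected post-switch TCE-exposed cases, N × H(1-s): clefts 32 × 0.0069 = 0.2 to 32 × 0.0743 = 2.4; NTDs 0.2 to 1.9; leukemias (third-trimester window) 14 × 0.0072 = 0.1 to 14 × 0.0771 = 1.1.

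**The case against.** The strongest reply is that the premise is open. The protocol calls the onset of contamination unknown, says in the Justification section that mothers' exposure is not yet known, and plans monthly reconstruction with extensive sensitivity analyses. That stands: the point is conditional. But the reference rule is already fixed, and a sensitivity analysis of the water model does not create concurrent unexposed births.

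A reader might infer that no mother before 1972 was unexposed. The documents do not support that. Eligibility is residence at any time in pregnancy while exposure is assigned by trimester, so some mothers were off base in the relevant window; well use was also intermittent.

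A reader might also infer that the TCE odds ratio is simply a before/after-1972 comparison. It is not. Hospital Point is described as a Hadnot Point housing area, TCE was found in the 1985 Tarawa Terrace sample, and the Holcomb area received Hadnot Point water for 12 days in 1985. If Tarawa Terrace carried TCE earlier, the pre-switch fraction falls. Nor is more than a quarter of births affected in every analysis: the third-trimester range starts at 23%.

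The housing shares are uncertain. The Introduction says the two contaminated supplies served slightly more than half of family-housing residents, which with T at 40% would need H of 10% or more, towards the lower end of the pre-switch fraction. Date of birth is collected, so birth year could enter through the confounder screen, and period detail may sit in an analysis plan not shown. Both are fair, but neither changes the stated reference rule. The expectation that most births were not exposed to TCE is no rebuttal: in Step 2, TCE-exposed births are about 12-25% of the total.

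**Conclusion.** The point holds in conditional form. If Hadnot Point was contaminated before the switch, the reference would contain almost no pre-switch births, about 23-31% of births would lack concurrent unexposed comparators, and about 60-96% of TCE-exposed births would fall in that period. A 1.5-fold period difference alone would then produce an odds ratio of about 1.3-1.5 for TCE and 1.11-1.15 for PCE. These sizes rest on equal births per month, the assumed housing shares, no TCE at Tarawa Terrace, and a period difference for which the protocol gives no figure.

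It might seem to follow that the post-1972 TCE stratum should carry the interpretation. It should not: with roughly 0-2 exposed cases per outcome and a standard error 1.4 to 4.4 times larger, it cannot. The PCE contrast is different, because its reference is unchanged and little precision is lost.

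**What to change.** In Data Analysis, state that once modeling is complete, exposure to TCE, to PCE and to neither will be tabulated by whether the exposure window falls before or after the Holcomb Boulevard switch. If pre-switch unexposed births are absent or nearly so:

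- **PCE:** interpret the post-switch contrast, where exposed and unexposed births are concurrent, and show the all-years odds ratio beside it.
- **TCE:** keep the all-years odds ratio, but report pre-switch Holcomb-area births as a separate TCE category, labelled as having no concurrent unexposed births. Give the post-switch TCE estimate alongside, with its number of exposed cases and a statement that it cannot carry the interpretation alone.

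If modeling shows clean Hadnot Point water before 1972, those births stay in the reference and nothing changes.

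The cost is a few sentences and one extra tabulation, with no new data. The PCE standard error rises by about 6-11%. For TCE the change gains no precision; it only shows how little concurrent information there is. Because mothers' exposure is not yet known, the rule can be set before any result is seen.

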A 1999-2002 ATSDR survey located 12,598 children born to parents who resided at Camp Lejeune at any time during pregnancy between 1968 and 1985. Children eligible for the survey were those born at 28 weeks or more gestation to mothers who were pregnant while they lived in base housing at Camp Lejeune during 1968-1985. Survey respondents were asked basic demographic questions as well as if the child was diagnosed with cancer before age 20 or if the child was diagnosed with a birth defect before age 5. If the child had cancer or a birth defect, the type of cancer or birth defect was also collected. Parental reports of cancer and birth defects are being verified by reviewing medical records. If medical records are not available to confirm a case, we will use other appropriate documentation such as the birth certificate, death certificate, or information obtained from a recent doctor's visit (e.g., a dental visit for potential cleft cases or physical therapy records for potential spina bifida cases) (Appendices VI, VII, VIII). The following cases of selected birth defects and cancers have been reported: 35 neural tube defects (NTDs), 42 oral cleft defects, and 22 childhood leukemias. To date, records have been obtained for 20 NTDs (15 confirmed as having NTDs; 5 confirmed as not having NTDs), 1 was ineligible, 1 refused, and 13 are still pending. Records have been obtained for 23 oral cleft defects (20 confirmed as having oral cleft defects; 3 confirmed as not having oral cleft defects), 3 refused, and 16 are still pending. Records have been obtained for 17 childhood leukemias (12 confirmed as having leukemia; 5 confirmed as not having leukemia), 2 were ineligible, and 3 are still pending.

Eligibility (Participant inclusion/exclusion criteria)

Potential cases consist of children with the following birth defects or childhood cancers who were born to mothers who resided at Camp Lejeune during their pregnancies between 1968 and 1985: NTDs (consisting of anencephaly and spina bifida), oral clefts (consisting of cleft lip with and without cleft palate and cleft palate), and childhood leukemias. Familial cases of leukemia, children who were 20 years of age or older when diagnosed with leukemia, or children who were 5 years of age or older when diagnosed with NTDs or oral clefts will be excluded. Only confirmed cases will be included in the primary analyses. We will consider doing a secondary analysis including unconfirmed cases.

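### The reason given for the optional secondary analysis, that the confirmed-only and the confirmed-plus-unconfirmed results enclose the true odds ratio, is not generally true and should be deleted

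*Protocol*

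**What the plan says.** Eligibility fixes the order of the analyses: "Only confirmed cases will be included in the primary analyses. We will consider doing a secondary analysis including unconfirmed cases". Data Analysis repeats that the secondary analysis will be considered and gives the reason: "the true odds ratio lies between the results obtained by analyzing only confirmed cases and confirmed and unconfirmed cases". The only argument offered is "because unconfirmed cases are not all negative (do not have the condition) or all positive (do have the condition").

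Study Population shows how much is unresolved. For NTDs, "records have been obtained for 20 NTDs (15 confirmed as having NTDs; 5 confirmed as not having NTDs"); of the other reports, "1 was ineligible, 1 refused, and 13 are still pending". For clefts, "Records have been obtained for 23 oral cleft defects (20 confirmed as having oral cleft defects; 3 confirmed as not having oral cleft defects"). Another 16 cleft reports are pending, and there were 3 refusals. For leukemia, 17 records were obtained (12 confirmed, 5 not), 2 reports were ineligible and 3 are pending.

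Data Analysis also says that findings will be interpreted by the size of the odds ratio and the exposure-response relationship, and that 90% confidence intervals will be calculated.

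**The concern.** The sentence gives the pair of analyses a property that they lack. Its argument would need one analysis to count every unconfirmed child as unaffected and the other to count every one as affected. The second does so. The first removes those children from the case group, which is a different operation.

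The case set that is wanted is the confirmed cases plus the true cases among the unconfirmed. Neither analysis uses that set, and nothing forces its odds ratio to lie between the other two.

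What is at stake is how a sensitivity analysis is read. Interpretation rests on the size of the odds ratio, and the two analyses share most of their cases, especially for leukemia (12 of at most 15). They will often agree closely for that reason alone. The sentence invites a reader to take that agreement as enclosing the truth.

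**Working it through.** The sentence states no figure, so there is none to reproduce. The check asks whether the property holds.

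**Inputs from the protocol.** Confirmed and pending: NTD 15 and 13, cleft 20 and 16, leukemia 12 and 3 (Study Population). Confirmed among reviewed: 15/20 = 75%, 20/23 = 87%, 12/17 = 71%. Exposure prevalence 40% (Sample Size, Power, and Precision of Risk Estimates), so control odds are 0.4/0.6 and OR = (exposed cases / unexposed cases) × 1.5.

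**Assumptions not in the protocol.** All pending children stay unconfirmed, they are true cases at the reviewed rate, and all take part.

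**1. Favorable case, no sampling error.** Let confirmation be unrelated to exposure and false cases be exposed like controls. Take a true OR of 2.5, so case exposure is 0.4 × 2.5 / (0.6 + 0.4 × 2.5) = 0.625.
- Confirmed-only: OR 2.50, already the truth.
- Combined NTD: expected true cases 15 + 0.75 × 13 = 24.75, false 3.25. Exposed share = (24.75 × 0.625 + 3.25 × 0.4)/28 = 0.599, giving OR 2.24.
- The same calculation gives 2.37 for clefts and 2.36 for leukemia.

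The truth is one end of the range, and the combined result is only diluted.

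**2. True unconfirmed cases differ in exposure, no sampling error.** NTD, confirmed OR 2.0 (exposed share 0.571), true unconfirmed OR 4.0 (0.727), false cases like controls.
- All true cases: (15 × 0.571 + 9.75 × 0.727)/24.75 = 0.633, OR 2.59.
- Combined: (15 × 0.571 + 9.75 × 0.727 + 3.25 × 0.4)/28 = 0.606, OR 2.31.
- Confirmed-only: 2.00.

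The value for all true cases, 2.59, lies outside 2.00–2.31.

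**3. Whole-number example, NTD.** Pending children assumed to be 10 true and 3 false.

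| Case set | Exposed / unexposed | OR |
|---|---|---|
| Confirmed | 9 / 6 | 2.25 |
| True pending | 7 / 3 | – |
| False pending | 0 / 3 | – |
| Confirmed + all pending | 16 / 12 | 2.00 |
| All true cases | 16 / 9 | 2.67 |

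2.67 lies outside 2.00–2.25. With one of the three false cases exposed, the combined set is 17/11, OR 2.32, and 2.67 is again outside.

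**4. How often this happens.** Simulation of 400,000 studies per setting, true OR 1.0 to 4.0, confirmation unrelated to exposure, false cases exposed like controls. The target is the odds ratio of all genuinely affected children in the same sample against the same controls, so the control sample cancels. That odds ratio lay between the two estimates in:
- NTD: 49–54% of studies
- Cleft: 54–58%
- Leukemia: 66–70%

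The ranges cover the true ORs tried and whether 0.5 is added to each cell.

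**5. Would simple imputation repair it?** Giving each pending child a 0.75 chance of being a case, regardless of exposure, turns the example in step 3 into 9 + 0.75 × 7 = 14.25 exposed and 6 + 0.75 × 6 = 10.5 unexposed. OR = 14.25/10.5 × 1.5 = 2.04. That lies inside 2.00–2.25 and further from 2.67 than confirmed-only does. On average such imputation is a down-weighted combined analysis and must fall between the same two estimates.

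**The case against.** The strongest defense is that little depends on the sentence. Only confirmed cases enter the primary analysis, and the secondary one is merely to be considered. No sample size, case definition or decision rule rests on the bracket, and no section commits to reporting the pair as limits. All of this stands, and it sets the severity.

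Three further points also stand.
- Pending is not the same as finally unconfirmed. Study Population plans further confirmation from certificates and recent doctor's visits, and the Discussion says confirmation is ongoing. The number unconfirmed at analysis is unknown.
- The example in step 3 is a fairly marked one. It misses by 2.67/2.25, about 19%, and none of three false cases being exposed has probability 0.6³ = 0.22 at 40% exposure.
- Sampling error is handled elsewhere, by the 90% intervals and the small-sample warning in the Discussion. The fair test is therefore step 4, which concerns case status. How often a population odds ratio falls between two point estimates from a dozen or two cases mostly measures sampling error.

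A reader might infer that the secondary analysis adds mainly false positives and so drags the odds ratio to 1. The protocol's own rates do not support that: at 71–87% confirmation, most of the added children would be true cases. Some dilution follows if false cases are exposed like controls, as in step 1.

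None of this rescues the sentence. It is stated as fact, without condition, and nothing else in the protocol qualifies it.

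**Conclusion.** The claim is wrong as a general statement. The two results are not bounds. In the favorable case the truth coincides with the confirmed-only result. When true or false unconfirmed cases differ in exposure, by chance or otherwise, it can lie outside both. At the protocol's counts the odds ratio of all genuinely affected children falls between them in roughly half of NTD, 55% of cleft and two thirds or slightly more of leukemia studies. Those frequencies rest on the pending children staying unconfirmed, being true cases at the reviewed rates, and being confirmed independently of exposure. The failure of the argument itself rests on none of these.

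Severity is minor to moderate. A reader might infer that the main results are compromised; they are not, because the confirmed-only primary analysis does not use the claim. That the pair would actually be reported as limits is also an inference, though a natural one, since the bracket is the stated reason for the analysis.

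**What to change.** In Data Analysis, delete the sentence saying that the truth lies between the two results. Keep confirmed cases as primary. Describe the confirmed-plus-unconfirmed analysis as a sensitivity analysis to case definition, report it with its own 90% confidence interval, and state that the two estimates are not limits.

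If a quantitative misclassification analysis is wanted, vary two things: the true-case proportion among unconfirmed children (around 15/20, 20/23 and 12/17) and the exposure of true versus false unconfirmed cases. Do not impute at a single confirmation rate without regard to exposure, for the reason in step 5 of the working.

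The cost is a few lines of protocol text and, if chosen, a short extra analysis. No new data are needed.
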